## 9.3 Definition of a Serious Adverse Event (SAE)

An adverse event is considered “serious” if in the view of the Investigator, it results in any of the following outcomes: death, a life threatening adverse event, inpatient hospitalization or prolongation of existing hospitalization, a persistent or significant incapacity or substantial disruption of the ability to conduct normal life functions, or a congenital anomaly/birth defect. Important medical events that may not result in death, be life-threatening, or require hospitalization may be considered serious when, based upon appropriate medical judgment, they may jeopardize the patient or subject and may require medical or surgical intervention to prevent one of the outcomes listed in this definition. Serious adverse events include seizures, encephalopathy, aseptic meningitis, optic and peripheral neuropathy, leukopenia, and a hypersensitivity reaction including Stevens-Johnson syndrome and toxic epidermal necrolysis.

## 9.4 Methods and Timing for Assessing, Recording, and Analyzing, Managing Safety Parameters

MTZ has been used for the treatment of TV for over 40 years. However, we will monitor adverse reactions in an ongoing basis and by the DSMB every 6 months.

The most serious adverse reactions reported in patients treated with MTZ have been convulsive seizures, encephalopathy, aseptic meningitis, optic and peripheral neuropathy, the latter characterized mainly by numbness or paresthesia of an extremity. Since persistent peripheral neuropathy has been reported in some patients receiving prolonged administration of MTZ, patients should be specifically warned about these reactions and should be told to stop the drug and report immediately to their physicians if any neurologic symptoms occur. The most common adverse reactions reported have been referable to the gastrointestinal tract, particularly nausea reported by about 12% of patients, sometimes accompanied by headache, anorexia, and occasionally vomiting; diarrhea; epigastric distress; and abdominal cramping. Constipation has also been reported. The following reactions have also been reported during treatment with MTZ: *Mouth*: A sharp, unpleasant metallic taste is not unusual. Furry tongue, glossitis, and stomatitis have occurred; these may be associated with a sudden overgrowth of *Candida* which may occur during therapy. *Hematopoietic*: Reversible neutropenia (leukopenia); rarely, reversible

Version: 11.0

Version date: 1/2/17

thrombocytopenia. *Cardiovascular*: Flattening of the T-wave may be seen in electrocardiographic tracings. *Central Nervous System*: Encephalopathy, aseptic meningitis, convulsive seizures, optic neuropathy, peripheral neuropathy, dizziness, vertigo, incoordination, ataxia, confusion, dysarthria, irritability, depression, weakness, and insomnia. *Hypersensitivity*: Urticaria, erythematous rash, Stevens-Johnson Syndrome, toxic epidermal necrolysis, flushing, nasal congestion, dryness of the mouth (or vagina or vulva), and fever. *Renal*: Dysuria, cystitis, polyuria, incontinence, and a sense of pelvic pressure. Instances of darkened urine have been reported by approximately one patient in 100,000. Although the pigment which is probably responsible for this phenomenon has not been positively identified, it is almost certainly a metabolite of metronidazole and seems to have no clinical significance.

*Other*: Proliferation of *Candida* in the vagina, dyspareunia, decrease of libido, proctitis, and fleeting joint pains sometimes resembling “serum sickness.” If patients receiving MTZ drink alcoholic beverages, they may experience abdominal distress, nausea, vomiting, flushing, or headache. A modification of the taste of alcoholic beverages has also been reported. Rare cases of pancreatitis, which generally abated on withdrawal of the drug, have been reported. Crohn’s disease patients are known to have an increased incidence of gastrointestinal and certain extra-intestinal cancers. There have been some reports in the medical literature of breast and colon cancer in Crohn’s disease patients who have been treated with metronidazole at high doses for extended periods of time. A cause and effect relationship has not been established. Crohn’s disease is not an approved indication for MTZ.

See Section 10 for a greater description of the monitoring process and <http://www.rxlist.com/flagyl-drug.htm> (medication insert) for more details on side effects.

### **9.4.1 Methods and Timing for Assessment**

Adverse events reported by participants will be recorded and reported to the institutional IRBs according to their reporting requirements. At each follow up visit, staff will inquire if any metronidazole was taken since last visit and if there were any adverse events from taking the medication. This information will be recorded in study data.

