### **8.6 Pregnancy Visit**

Women will not be enrolled if they are pregnant. If they become pregnant during the course of the study, it will not affect study enrollment because they would have already been treated for TV. If it is determined that the participant was pregnant at the time of treatment, the woman and her child will be followed according to the site specific regulatory requirements.

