## 9. ASSESSMENT OF SAFETY

### 9.1 Specification of Safety Parameters

Metronidazole in the 2gm dose is an FDA approved treatment for TV. The 7 day 500mg BID dose is recommended in the CDC treatment guidelines for TV, however, is not currently FDA approved.

There are three main safety concerns:

- 1) Adverse drug reactions including, allergy, hypersensitivity reaction, or other adverse reaction to metronidazole, alcohol use within 24 hours of taking medication, and contra-indications with other medications.
- 2) Pregnancy in a woman who tested negative at entry.
- 3) That discussing their infection with partners may put participants at risk for verbal or physical abuse by disclosing their STI to their partners.

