## 9.2 Definition of an Adverse Event (AE)

Vomiting within 2 hours of consumption of the medication with no other signs of allergic reaction to MTZ will not be considered an adverse event but will be documented. Adverse events include eye pain, sudden vision changes, sore throat, persistent fever, unusual bleeding/bruising, severe stomach pain, persistent nausea/vomiting, fatigue, hypersensitivity reaction or other adverse reaction to MTZ.

Any form of intimidation, verbal or physical abuse will be considered an adverse event.

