### **9.5.1 Specific Serious Adverse Event Requirements**

All serious adverse events will be recorded on the case report form as SAE. Investigators at the clinical site who are the study physicians will work with the Principal Investigator to resolve the SAE. The study physical will follow up with participants and report resolution success to the PI.

Any AE that meets the division's or protocol-specific expedited (or serious) adverse event reporting criteria must be submitted to the NIAID's pharmacovigilance contractor, at the following address, using the appropriate form (if applicable):

DMID

Clinical Research Operations and Management Support (CROMS)[name]

[name], USA

SAE Hot Line: [name]

SAE [contact]

SAE Email Address: [contact]

The study clinician will complete an Expedited or Serious Adverse Event Form within the following time guidelines:

All deaths and immediately life threatening events, whether related or unrelated, will be recorded on the Expedited or Serious Adverse Event Form and faxed/electronically communicated within 24 hours of site awareness.

Adverse events other than death and immediately life threatening events, that meet expedited reporting criteria, regardless of relationship, will be faxed/electronically communicated by the site within 72 hours of becoming aware of the event.

Version: 11.0

Version date: 1/2/17

Other supporting documentation of the event may be requested by the pharmacovigilance contractor and should be provided as soon as possible.

All reportable AEs will be followed until satisfactory resolution or until the Principal Investigator or Sub-investigator deems the event to be chronic or the participant to be stable.

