### **9.6 Reporting of Pregnancy**

Interventions are given at baseline visit only. All participants found to be TV positive at a follow up visit, will be referred to clinic providers to be retreated at the provider’s discretion. The study does not treat participants or their partners with medication at follow up visits. Women who become pregnant during the study remain eligible for study participation. Pregnancy will not be recorded as an adverse event but will be noted in study charts and the pregnant participant and their child may be followed according to the site IRB regulations.

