# **10. Clinical Monitoring Structure**

## **10.1 Site Monitoring Plan**

The Principal Investigator and Tulane study staff under the direction and supervision of the PI, will conduct regular site monitoring to ensure human subject protection and that study procedures are being conducted as per protocol and Manual of Procedures as outlined in section 12.0. For the first 4 months of enrollment, weekly conference calls will be held with investigators and study personnel at sites to ensure start up activities are following protocol, any questions can be answered, and clinic flow and specific clinical issues can be addressed. The PI and Program Manager are available at any time via email or cell phone to address any urgent issues. Quarterly site visits will be conducted by the PI, or her designee. At these visits, at least 10% of study charts will be pulled and reviewed, all consent forms will be reviewed and consent procedures will be discussed. There will also be a systematic review of enrollment statistics (i.e., number of eligible patients, refusal log, ineligibility log). Weekly data transfer to the research office at Tulane University will allow the program manager to review data collected for any errors or discrepancies and report back to sites to resolve any inconsistencies.

Women will be systematically asked if they experienced any of the common side effects on the TOC CRF.

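### The scheduled safety questions described cover drug effects only; none is described for partner abuse, pregnancy, or serious events reportable whatever their cause

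*Combined protocol and SAP*

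**What the plan says.** All references are to the combined protocol and SAP.

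**What is monitored.** Section 9.1 lists three main safety concerns: drug reactions, pregnancy ("Pregnancy in a woman who tested negative at entry"), and abuse by a partner after disclosure. Section 9.2 adds: "Any form of intimidation, verbal or physical abuse will be considered an adverse event". Section 9.6 says pregnancy is not an adverse event but is to be noted in the charts.

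**What must be reported.** Section 9.5.1 states: "All deaths and immediately life threatening events, whether related or unrelated, will be recorded", within 24 hours of site awareness. Other events meeting the expedited criteria go in within 72 hours, again regardless of relationship.

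**What is asked.** Section 9.4.1 opens with "Adverse events reported by participants will be recorded and reported to the institutional IRBs". It then says that at each follow-up visit staff ask whether metronidazole was taken and "if there were any adverse events from taking the medication". Section 10.1 adds: "Women will be systematically asked if they experienced any of the common side effects on the TOC CRF". Section 9.4.1.1, on recording serious events, speaks only of serious events to metronidazole.

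**Other routes.** Participants carry a contact card that mentions adverse events (8.2). Medical records are abstracted at each visit when available (7.1). Interim clinic visits are noted (8.7).

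**The concern.** Sections 9.1, 9.2 and 9.5.1 set a wide scope: drug reactions, pregnancy, abuse, and serious events of any cause. The scheduled inquiry in 9.4.1 is limited to events that the woman herself links to the medication. A woman threatened after telling a partner of her infection, or admitted to hospital for something she does not connect with the tablets, can truthfully answer no.

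Section 10.2 has the DSMB review adverse and serious adverse events at its meetings. What the board sees depends on what is elicited. If abuse, pregnancy and unrelated serious events come in only when volunteered or found in a record, a low count may mean few events or few disclosures, and the data could not tell the two apart.

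**Working it through.** The plan gives no figure on this point, so the check sets the sections side by side.

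**Step 1. Match each commitment to a scheduled question.**

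| Event type | Where the plan commits to it | Scheduled question described |
|---|---|---|
| Drug reactions | 9.1 (main concern), 9.2 | Yes: 9.4.1 and 10.1 |
| Pregnancy | 9.1 (main concern), 9.6 (note in charts) | None |
| Partner abuse | 9.1 (main concern), 9.2 (adverse event) | None |
| Serious events of any cause | 9.5.1 | None |

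Two scheduled safety questions are described, both on drug effects. Of three main concerns, one is covered and 3 − 1 = 2 are not. The number of described questions on serious events regardless of relationship is zero.

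**Step 2. Check whether the visit content fills the gap.** Section 8.3 lists the survey and testing for *T. vaginalis* and bacterial vaginosis at follow-up; no pregnancy test is listed. The follow-up survey is described as covering adherence (6.2), partner treatment, sexual exposure and condom use (11.13). Neither section mentions abuse, pregnancy or hospital admission.

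**Step 3. Look at the other routes.** Volunteered reports and the contact card (9.4.1, 8.2) depend on the woman raising the matter. Record abstraction (7.1) depends on records being available. Section 8.7 covers visits to the study clinic, not care elsewhere. Section 9.6 says where pregnancy is written down, not how staff learn of it. These are real routes, but each is passive or conditional.

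**Step 4. Timing.** The first scheduled inquiry is at the TOC visit, 3 to 12 weeks after visit 1 in the single-dose arm and 4 to 13 weeks in the 7-day arm (section 8 visit schedule). Visit 3 may be scheduled only for women who are NAAT-positive and culture-negative at TOC. For every other woman TOC is the only scheduled inquiry.

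**Step 5. Who judges causality.** Section 9.4.2 puts relation to metronidazole on the event form, and section 14.1 requires events to be assessed for causality and reviewed by the site investigator or study manager. The 9.4.1 question places a filter ahead of that assessment, because the woman must first attribute the event. The 10.1 question does not ask her to attribute anything, but it is limited to common side effects.

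**Step 6. Reporting clocks.** The 24-hour and 72-hour limits in 9.5.1 run from site awareness. An event that is never elicited may never start the clock. Section 9.4.1.1, limited to serious events to metronidazole, is also narrower than 9.5.1.

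**The case against.** The strongest reply is that the documents do not include the follow-up survey items, the TOC form, the event form or the manual of procedures. Any of these may already ask about abuse, pregnancy or hospital admission. That stands. A reader might infer that these events are never asked about; the text supports only that no scheduled question is described.

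Nor does the plan leave the events without a route. Volunteered events are recorded with no attribution limit, and record abstraction and noted clinic visits add to that. It would be wrong to say that only spontaneous reports are captured.

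Three stronger readings are tempting and should not be drawn:

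- **A conflict over following pregnancies.** Section 8.6 says "If it is determined that the participant was pregnant at the time of treatment, the woman and her child will be followed", while section 9.6 says "the pregnant participant and their child may be followed according to the site IRB regulations". These can be read as two groups: women already pregnant at treatment, and women who conceive later. Section 2.3.1 also speaks of the latter. A firm rule for one and a discretionary rule for the other can stand together.
- **Follow-up too short to see a congenital anomaly.** The 21-week limit in the protocol summary is the time to complete study visits. Sections 2.3.1, 8.6 and 9.6 separately allow mother and child to be followed.
- **A count of missed events.** The documents give no rate of abuse or of pregnancy in this population, so any count would rest on assumed rates alone.

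It is also fair that pregnancy is deliberately not an adverse event, that testing before randomization and contraceptive advice reduce exposure, and that the 9.5.1 duty can be met as written because it starts at awareness. Finally, a question at TOC cannot detect deaths or reach women who do not return: section 11.7 expects 1332 of 1664 to be evaluable, leaving 1664 − 1332 = 332.

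**Conclusion.** The point holds as a rule drawn too narrowly. The two scheduled safety questions described concern drug effects. Two of the three main safety concerns, and serious events reportable regardless of relationship, have no described scheduled question and depend on volunteered reports, noted interim visits or available records. Followed as written, section 9.4.1 would tend to under-capture them, and low counts could not be read as reassurance. The drug-attributed wording in 9.4.1 and 9.4.1.1 must be reconciled with 9.1, 9.2 and 9.5.1.

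The size is stated as coverage (one of three main concerns, and none for serious events of any cause), not as a number of events. The conclusion assumes that the unseen forms do not already carry the missing items. If they do, what remains is to say so in the protocol. It does not bear on the efficacy analysis. This is a cheap improvement.

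**What to change.** In section 9.4.1, and on the existing TOC form or survey, replace the drug-attributed question with three unattributed items:

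1. Any new medical problem or hospitalization since the last visit, with relationship then assigned by study staff as sections 9.4.2 and 14.1 already provide.
2. Any intimidation or verbal or physical abuse, asked in private or by computer-assisted self-interview.
3. Whether she is or has been pregnant since enrollment, with the date of her last menstrual period.

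Keep the side-effect question in 10.1. Bring the wording of 9.4.1 and 9.4.1.1 into line with 9.1, 9.2 and 9.5.1. If the survey or form already contains these items, cite them in 9.4.1; no new question is then needed.

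The cost is a few more questions, a wording amendment, and more unrelated events to record and grade. The change reaches only women who attend follow-up, so the passive routes are still needed for the rest.

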#### **9.4.1.1 AE/SAE Grading and Relationship Assignment**

Serious adverse events to metronidazole by participants will be recorded by severity and relation to dosing at each clinical site. These will be immediately reported to the Lead PI, other Investigators, and institutional IRBs according to their reporting requirements. DSMB will be notified.

### **9.4.2 Recording/Documentation**

A standard event reporting form will be used by all sites. In the event of an adverse event, it will be mandated that this form must be filled out by study personnel within 24 hours of the

Version: 11.0

Version date: 1/2/17

reporting of the event and sent to the investigators for review. A complete description of the adverse event will include time of onset, length of event, relation to metronidazole, and resolution and severity of event.

### **9.4.3 Analysis/Management**

Adverse events will be considered in the analysis of the endpoint in cases where they affect adherence to the drug.

## **9.5 Reporting Procedures**

The Lead PI and the site PI(s) will discuss the reported event and decide if it meets the standard for institutional IRB reporting of adverse events. If so, they will report the event according to their IRB reporting requirements. The DSMB will also be notified of the AE or SAE by the Lead PI. The site investigators will be notified to discuss the event and resolution with the patient to make certain the participant is treated appropriately.

### **9.5.1 Specific Serious Adverse Event Requirements**

All serious adverse events will be recorded on the case report form as SAE. Investigators at the clinical site who are the study physicians will work with the Principal Investigator to resolve the SAE. The study physical will follow up with participants and report resolution success to the PI.

Any AE that meets the division's or protocol-specific expedited (or serious) adverse event reporting criteria must be submitted to the NIAID's pharmacovigilance contractor, at the following address, using the appropriate form (if applicable):

DMID

Clinical Research Operations and Management Support (CROMS)[name]

[name], USA

SAE Hot Line: [name]

SAE [contact]

SAE Email Address: [contact]

The study clinician will complete an Expedited or Serious Adverse Event Form within the following time guidelines:

All deaths and immediately life threatening events, whether related or unrelated, will be recorded on the Expedited or Serious Adverse Event Form and faxed/electronically communicated within 24 hours of site awareness.

Adverse events other than death and immediately life threatening events, that meet expedited reporting criteria, regardless of relationship, will be faxed/electronically communicated by the site within 72 hours of becoming aware of the event.

Version: 11.0

Version date: 1/2/17

Other supporting documentation of the event may be requested by the pharmacovigilance contractor and should be provided as soon as possible.

All reportable AEs will be followed until satisfactory resolution or until the Principal Investigator or Sub-investigator deems the event to be chronic or the participant to be stable.

## REGULATORY REPORTING FOR STUDIES CONDUCTED UNDER NIAID-SPONSORED IND

Following notification from the investigator, the IND sponsor/Lead PI, will report events that are both serious and unexpected and that are associated with Study Agent(s)/Intervention(s) to the FDA and other applicable health authorities within the required timelines as specified in 21 CFR 312.32: fatal and life threatening events within 7 calendar days (by phone /fax/electronic communication) and all other serious adverse events in writing within 15 calendar days. All serious events designated as “not associated” to Study Agent(s)/Intervention(s), will be reported to the FDA at least annually in a summary format.

### **9.6 Reporting of Pregnancy**

Interventions are given at baseline visit only. All participants found to be TV positive at a follow up visit, will be referred to clinic providers to be retreated at the provider’s discretion. The study does not treat participants or their partners with medication at follow up visits. Women who become pregnant during the study remain eligible for study participation. Pregnancy will not be recorded as an adverse event but will be noted in study charts and the pregnant participant and their child may be followed according to the site IRB regulations.

### **9.7 Type and Duration of the Follow-up of Participants after Adverse Events**

Because this is a phase III study of medications that are being used for their intended purpose, we anticipate that serious adverse events will be a rare occurrence. Participants who experience unresolved nausea and/or vomiting or allergic reaction will be referred to the clinic providers and they will provide care according to clinic protocol.

